Our institution has been using RiaSTAP on this high-risk patient population since April 2013. In a separate, retrospective analysis our group has compared a group of 50 patients who received RiaSTAP with 50 age, diagnosis and procedure matched patients prior to April 2013. Our analysis demonstrates that there is a statistically significant reduction in the need for FFP and cryoprecipitate, without an increase in thromboembolic events, when RiaSTAP is used at a dose of 70 mg/kg.¹⁵

Criteria For Subject Selection

Number of subjects: 30

Gender of subjects: There are no gender-based enrollment restrictions for this study. Gender distribution should reflect the gender distribution of the patient population and the gender distribution of Congenital Heart Disease (CHD) in general which is slightly skewed towards male patients in a 60:40 ratio of males to females.

Age of Subjects: Age will range from full term (at least 37 weeks gestational age) newborns to 12 months old, inclusive.

Racial and Ethnic Origin: There are no racial and ethnic restrictions for this study.

Inclusion Criteria: All neonatal and infant cardiac patients presenting for open-heart surgery at Nicklaus Children's Hospital will be eligible for enrollment in the study.

Exclusion criteria: Patients who fall outside of the age range for the study will be excluded. Patients known to have had an anaphylactic or severe reaction to the drug or its components will not be enrolled. At the time of the rewarming ROTEM, any patient with a FIBTEM MCF > 15 mm, will be excluded.

Vulnerable subjects: Patients in the study population are neonatal and infant cardiac surgical patients and are considered vulnerable subjects.

Methods and Procedures

Randomization:

We plan to enroll 30 neonates and infants scheduled for elective cardiac surgery. Patients will be randomized to one of two groups with 15 patients in each group; Group 1 will receive an infusion of RiaSTAP, right after the termination of CPB at a dose of 70 mg/kg and

Group 2 will receive a placebo of Normal Saline 0.9% (NS) during the same time period. The volume of NS will be calculated to be the same volume that would be used IF the patient were receiving RiaSTAP. This will be the only difference between the groups.

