Both Groups will receive the normal standard of care both before and especially after this event. This will be the only event that is different for the two groups. To avoid selection bias, the Pharmacy will perform the randomization using Research Randomizer. Briefly, for each patient, a randomly generated integer between 1-30 will be produced. If the number is even, the patient will be assigned to Group 1. If the number is odd, the patient will be assigned to Group 2. The randomization process and schedule will be provided by the Principal Investigator's office, but the actual patient assignment will be done by Pharmacy.

All operating room and ICU personnel will be blinded to the patient's Group assignment. The only persons who will have access to the identity of the Group assignment from the time of randomization until 24 hours after surgery will be members of the Pharmacy staff. NONE of these individuals will be involved in patient care. The DSMB will be unblinded AFTER the study treatment period concludes (24 hours after surgery).

Endpoints:

Primary efficacy endpoints will be estimated as follows:

- postoperative bleeding (EBL) during the first 24 hours (hr) after surgery (cc/kg),
- the identity and total volume of transfused blood products (cc/kg) given in the peri-operative period, separated out into its components,
- hemoglobin concentration 2 hr. and 24 hr. after surgery and
- effects of fibrinogen infusion on global hemostasis 2 hr. and 24 hr. after surgery (PT, PTT, INR, fibrinogen level, platelet count and ROTEM analysis).

Post-operative period begins after the patient leaves the operating room. The need for Factor VII use and dose will also be included as a primary end point. Factor VII is typically used only if there is profuse bleeding not amenable to component transfusion therapy.

Secondary end points will include:

- the number of post-op hours requiring ventilator support,
- Length of Stay (LOSH) in the hospital,
- Length of Stay (LOS ICU) in the Cardiac Intensive Care Unit (CICU) and
- the need for re-exploration for bleeding within the first 12 hours.

The primary safety endpoints that will be monitored are the presence of a clinical adverse events. Clinical adverse events (AEs) are defined as any clinical signs of central or peripheral thromboembolism, respiratory or circulatory failure, or allergic reactions during hospital stay. It will also include infection with a blood-borne pathogen.

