Patients under 10 kg in body weight will have the CPB pump primed with one unit of Packed Red Blood Cells (PRBC) and 200 cc Fresh Frozen Plasma (FFP). In patients over 10 kg a pure crystalloid prime will be used. Target hemoglobin (Hg) while on CPB will be 9 gm/dL, but the transfusion trigger for additional units of PRBC will be 7 gm/dL.

Drug protocol:

The following laboratory studies will be obtained prior to surgery: Complete Blood Count (CBC), Prothrombin time (PT), International Normalized Ratio (INR), Partial Thromboplastin time (PTT), Platelet count, and a Fibrinogen level; an electrolyte profile will also be done. An Activated Clotting Time (ACT) and a Thromboelastometry analysis [REDACTED], a device that assesses the viscoelasticity of whole blood and other parameters, will be done after an A-line is placed (Figure 1).

A blood products transfusion algorithm was developed based on four previous studies published in the literature, modified for pediatrics¹⁶¹⁷¹⁸¹⁹ (Figure 2). Blood is measured in the cell saver reservoir and the suction canister every fifteen minutes while in the OR. Clinically significant bleeding, requiring treatment, will be defined as a rate in excess of 10 cc/kg/hr calculated every 15 minutes while in the OR. Calculations will be done every 60 minutes in the CICU.

After rewarming, but prior to the termination of CPB a ROTEM analysis will be done. Platelets or FFP will be administered at this time, while still on CPB, if the ROTEM results indicate a deficiency of either component. Then immediately after the termination of CPB, RiaSTAP or NS will be administered depending on the group assignment. Then, as per routine care, a ROTEM analysis and fibrinogen level will be assessed and the transfusion algorithm will be continued. *If the ROTEM indicates a fibrinogen deficiency, cryoprecipitate will be given.* Thereafter, as per routine care, a ROTEM analysis will be done at least every 30 minutes while in the OR or sooner at the discretion of the OR team. Once the patient leaves the OR a ROTEM will be done at least every 60 minutes for the first six hours or until clinically significant bleeding has stopped, whichever comes first; ROTEMs can be done more frequently at the discretion of the ICU staff caring for the patient. The blood products transfused after separation from CPB will be based on the protocol below (Figure 3). Dosing amounts of the required component therapy will be based on the formula below:

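### The even/odd rule, as written, does not guarantee the stated 15 patients per group; separately, the 2 h and 24 h laboratory analyses name no baseline covariate

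*Combined protocol and SAP*

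**What the plan says.** **Allocation.** Under Methods and Procedures, Randomization, the sample is 30 and "Patients will be randomized to one of two groups with 15 patients in each group". The mechanism follows: "for each patient, a randomly generated integer between 1-30 will be produced". Then: "If the number is even, the patient will be assigned to Group 1"; an odd number means Group 2. The description is introduced as a brief one. "The randomization process and schedule will be provided by the Principal Investigator"'s office, while Pharmacy makes the actual assignment. Methods to Minimize Bias names Research Randomizer again and refers back to this section without adding a restriction.

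**Exclusion during surgery.** Under Exclusion criteria: "At the time of the rewarming ROTEM, any patient with a FIBTEM MCF" above 15 mm is excluded. The Schedule of Events lists randomization and pharmacy preparation only as intraoperative. It does not say whether they come before or after that check.

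**Laboratory endpoints.** Hemoglobin, PT, PTT, INR, fibrinogen, platelets and ROTEM are primary endpoints at 2 h and 24 h. The Drug protocol also collects baseline values: "The following laboratory studies will be obtained prior to surgery", followed by a list covering the blood count and coagulation tests, with a thromboelastometry run once the arterial line is in. Statistical Analyses names the t-test, Fisher's exact test, and repeated-measures ANOVA followed by t-tests if the group or the interaction term is significant. It names no covariate.

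**The concern.** The stated group sizes do not follow from the stated rule. Pharmacy has to carry out the rule, and cannot tell from it whether a number may come up twice. If numbers may repeat, the arms will usually not be 15 and 15. The plan also does not say what becomes of the number of a patient excluded at rewarming, so two pharmacists could follow the text and produce different lists.

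The laboratory matter is independent of allocation and concerns precision only. Each measure has its own pre-operative value, and the analysis makes no stated use of it. With 15 per group, a moderately predictive baseline would be worth having.

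**Working it through.** **Inputs.** From the protocol: N = 30, 15 per group, integers 1 to 30, significance at p ≤ 0.05. Assumed, because the documents give none: two-sided testing, an effect of 0.8 SD, a 2 h to 24 h correlation of 0.5, and a correlation r between the pre-operative and later values of 0 to 0.5.

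**1. Reproducing 15 per group.** The range 1 to 30 holds 15 even and 15 odd integers. If each is used exactly once, the split is 15:15 with certainty. The plan's figure is reproduced only on this reading, which the text does not state.

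**2. Literal reading.** Each draw is even with probability 15/30 = 0.5, so the size of Group 1 is Binomial(30, 0.5), with SD √(30 × 0.25) = 2.74.
- Exactly 15:15: C(30,15)/2³⁰ = 155,117,520/1,073,741,824 = 0.1445
- 18:12 or worse (at least 3 from 15): 0.3616
- 20:10 or worse (at least 5 from 15): 0.0987

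**3. Power cost.** Efficiency relative to 15:15 is 4·n₁·n₂/900: 0.96 at 18:12, 0.889 at 20:10, and 0.967 on average. Noncentral-t power of the two-sample t-test:

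| Assumed effect | 15:15 | Averaged over splits | Loss (points) |
|---|---|---|---|
| 0.5 SD | 26.2% | 25.5% | 0.7 |
| 0.8 SD | 56.2% | 54.7% | 1.4 |
| 1.0 SD | 75.3% | 73.8% | 1.5 |
| 1.2 SD | 88.7% | 87.6% | 1.1 |

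(Losses are taken before rounding.)

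**4. Predictability of a shuffled list.** Someone who knows past assignments and always guesses the arm that is behind is right, for a block of size b, at rate [b/2 + (2ᵇ/C(b, b/2) − 1)/2]/b. With b = 30, 2³⁰/C(30,15) = 6.92, so the rate is (15 + 5.92/2)/30 = 0.599. By position (simulated lists) it is 0.551 over the first 20 patients and 0.694 over the last 10. Independent draws give 0.50. Three blocks of 10 give 0.653.

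**5. Laboratory values.** In units of the single-time SD, the mean of the 2 h and 24 h values has variance (1 + 0.5)/2 = 0.75. Without a baseline, the standardised effect is 0.8/√0.75 = 0.924, and group-test power at 15 per group is 68.5%. With the pre-operative value as covariate the residual variance is 0.75 − r², with one fewer degree of freedom (27). Power from 40,000 simulated trials per setting:

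| r | Residual variance | Power with covariate |
|---|---|---|
| 0 | 0.75 | about 67% |
| 0.2 | 0.71 | about 69% |
| 0.3 | 0.66 | about 73% |
| 0.5 | 0.50 | about 83% |

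**6. The group-or-interaction gate.** With two time levels, the group test uses the mean of the two values and the interaction test uses their difference. Under no effect the chance that at least one is significant is about 1 − 0.95² = 9.75%. Simulation gives 9.5 to 10.0% without the covariate and 9.5 to 10.1% with it.

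**The case against.** The strongest reply is that the authors meant each integer to be used once. The description is announced as brief, a schedule is mentioned, and the range 1 to 30 matches both the sample size and the 15:15 split. That reading is plausible, and it is why the claim is only that the rule does not guarantee 15:15. It does not remove the need for a sentence, because drawing a number for each patient also describes a fresh draw with repeats allowed.

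Several stronger readings are tempting, and the documents do not support them.
- **Biased allocation.** A reader might infer bias from unequal arms. Each patient has probability 0.5 of either group under both readings, and the comparison stays valid.
- **A list held by the investigators.** The schedule from the Principal Investigator's office could be taken for the allocation list. The same section has Pharmacy make the assignments and says of Pharmacy staff: "The only persons who will have access to the identity of the Group assignment" until 24 hours after surgery. No conflict is shown.
- **Lost sample size at rewarming.** This needs both assignment before the FIBTEM check and no replacement. Neither is stated, and no exclusion rate is given. What stands is missing detail.
- **A pre-operative value diluting the ANOVA.** This would follow if it were a third time level. The endpoints are defined only at 2 h and 24 h, so two levels is the natural reading.
- **Fewer false openings with a covariate.** Step 6 shows that the gate opens about 10% of the time under no effect either way.

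On the covariate, it is fair to object that the correlation may be weak. The Cardiopulmonary Bypass section says: "Patients under 10 kg in body weight will have the CPB pump primed with one unit of Packed Red Blood Cells" and 200 cc of plasma, and platelets or plasma may be given on bypass. Either could loosen the link between pre-operative and later values.

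**Conclusion.** The inconsistency is real and minor. Under the literal rule the stated 15 per group is met exactly in 14.4% of trials, with 18:12 or worse in 36% and 20:10 or worse in 9.9%. These figures are exact and rest only on the text. The average power cost, about 1.4 points at 0.8 SD, rests on an assumed effect and two-sided testing; it stays between 0.7 and 1.5 points for effects of 0.5 to 1.2 SD. Validity is not in question.

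The place of assignment relative to the rewarming exclusion is unspecified and should be settled in the same edit.

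The laboratory point is a separate, optional gain in precision. Its size depends on a correlation that the documents do not give: about 4 points at 0.3, about 15 at 0.5, nothing near 0.2, and a loss of about 1.5 points at zero. The unadjusted analysis is valid as it stands.

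**What to change.** **Allocation.** Make the two statements in the Randomization section agree, in one of two ways.
1. State that Pharmacy uses the integers 1 to 30 in shuffled order, each once, on a list that only Pharmacy holds. This gives 15:15 for 30 assigned patients. The cost is predictability: about 60% correct guesses overall and 69% over the last 10 patients. This matters here because Methods to Minimize Bias accepts that ROTEM values may reveal the study drug to anesthesiologists who are themselves investigators, and Process of Consent lets the Principal Investigator and Sub-Investigators obtain consent. People who recruit may therefore be able to infer past assignments.
2. Keep independent draws and change the sizes to an expected 15 per group. Guessing stays at 50%, for about 1.4 power points at 0.8 SD.

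Either is defensible; the sponsor should choose one and say so.

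**Exclusion at rewarming.** In the same sentence, state that assignment follows the FIBTEM check, or that the number of a patient excluded there passes to the next patient. The first shortens Pharmacy's preparation time; the second may waste a prepared dose.

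**Laboratory analyses.** Under Statistical Analyses, keep the repeated-measures model with 2 h and 24 h as the only time levels. Add each measure's own pre-operative value as covariate, and use it in the follow-up comparisons too. For ROTEM, name which reading is the baseline. The data are already collected, so the cost is wording and about 1.5 power points if the baseline proves uninformative.

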RiaSTAP is a purified fibrinogen concentrate derived from the plasma of healthy donors using the Cohn/Oncley cryoprecipitation procedure¹¹. The FDA approved RiaSTAP in 2009 under the accelerated approval regulations for orphan drugs¹². RiaSTAP is indicated for the treatment of acute bleeding in patients with congenital fibrinogen deficiency (CFD), including afibrinogenemia and hypofibrinogenemia and has several advantages over FFP and cryoprecipitate. First, the fibrinogen concentration is standardized. Second, it is stored as a lyophilized powder at room temperature and can be reconstituted quickly with sterile water. Third, infusion volumes are low, allowing for rapid administration without delays for thawing or cross-matching¹³. Fourth, the manufacturing processing of RiaSTAP includes solvent/detergent exposure or pasteurization, thus minimizing the risk of viral transmission. RiaSTAP is manufactured from cryoprecipitate into a glycine precipitate, which is then further purified by multiple precipitation/adsorption steps. The manufacturing process has been demonstrated to reduce the risk of virus transmission in an additive manner: cryoprecipitation, Al(OH)₃ adsorption/glycine precipitation/Al(OH)₃ adsorption, heat treatment (60° C for 20 hours in an aqueous solution), and two subsequent glycine precipitation steps (initial and main glycine precipitation steps). These steps have been validated independently in a series of in vitro experiments for their capacity to inactivate and/or remove both enveloped and non-enveloped viruses. However, there is still a small risk of acquiring an infectious disease, despite the testing of plasma donor and the above outlined steps, mostly due to the transmission of prions, the causative agent in Creutzfeldt-Jakob disease. Finally, RiaSTAP does not contain any citrate so the risk of decreased myocardial contractility and hypotension is minimized.

RiaSTAP is contraindicated in patients who have manifested severe, immediate hypersensitivity reactions. Thrombosis has also been reported in patients treated with

RiaSTAP, but the risk appears to be low¹⁴. However, Jakobsen, Tang and Folkersen reported an increased risk of neurological thromboembolic complications and renal failure in their retrospective review of 1,876 adults undergoing coronary artery bypass graft surgery (CABG) treated with fibrinogen concentrate.

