Primary efficacy endpoints will be postoperative bleeding during the first 24 hours (hr) after surgery (cc/kg), the total volume and identity of transfused blood products (cc/kg), hemoglobin concentration 2 hr. and 24 hr. after surgery and effects of fibrinogen infusion on global hemostasis 2 hr. and 24 hr. after surgery (PT, PTT, INR, fibrinogen level, platelet count and ROTEM analysis). Secondary end points will include the number of post-op hours requiring ventilator support, Length of Stay (LOS) in the Cardiac Intensive Care Unit (CICU), the need for re-exploration for bleeding within the first 12 hours, and LOS in the hospital. The need for Factor VII use and dose will also be included.

The primary safety endpoint is a clinical adverse event. Clinical adverse events are defined as:

1. Any clinical signs of central or peripheral thromboembolism. This will then be confirmed by Doppler ultrasound. Assessments will be made once per shift (once every eight hours)
2. Respiratory or circulatory failure. Parameters of respiration, like respiratory rate (RR), end-tidal CO₂ (ETCO₂) and circulation, like heart rate (HR), rhythm, blood pressure (BP), arterial oxygen saturation (SpO₂) are monitored continuously while in the ICU. Respiratory failure will be defined as the need for reintubation after extubation. Circulatory failure will be defined as cardiac arrest.
3. Allergic reactions during hospital stay. These will include signs or symptoms like urticaria, wheezing, angioneurotic edema, and anaphylaxis.
4. Infection with a blood borne pathogen. Manifestation of an infection with a blood borne pathogen is unlikely to occur during the study treatment period, which ends 24 hours after the end of surgery. If this were to occur, it would not manifest itself for weeks or even months.

Patients will be assessed once per shift (once every eight hours) for signs of thromboembolism. Any evidence of thromboembolism will warrant a vascular ultrasound to assess the integrity of the vessel.

Adverse events will be monitored until discharge.

All patients will be assessed for signs and symptoms of thromboembolism, per routine care. Specifically, patients will be assessed for signs and symptoms of central and arterial

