To avoid selection bias, patients will be randomized to their treatment assignment group by the research pharmacists using the Research Randomizer. The randomization procedures are detailed in the Methods and Procedures section of this protocol. All operating room and ICU personnel will be blinded to the patient's Group assignment. An intensive care nurse blinded to group assignment will record postoperative bleeding every hour. Since the study is blinded and the practitioners caring for the patient will not know if the subject received the study drug or placebo, for the study treatment period (ending 24 hours after surgery), the Cardiac Intensive Care Unit staff will monitor the incidence of adverse thromboembolic events and intervene with routine care, if necessary. In order to maintain patient safety, the ROTEM analyses must be interpreted by the anesthesiologist caring for the patient in order to guide transfusion therapy. This is the standard of care and an integral part of the protocol. The hospital staff anesthesiologists are also investigators in the study including the Principal Investigator. As part of routine care, if the ROTEM results indicate a deficiency of platelets or FFP, either component will be administered while still in the OR. In addition, if the ROTEM indicates a fibrinogen deficiency after termination of CPB, cryoprecipitate will be given. After review of the ROTEM values, the identity of the study drug may be discernable. In order to avoid the ascertainment bias from this knowledge, study data will be analyzed by a biostatistician independent of the investigator prior to any presentation or publication of study results. The biostatistician will be blinded to the study treatment assignment.

Statistical Analyses

All quantitative measures will be analyzed using descriptive statistics [mean +/- standard deviation (SD), etc.]. Treatment and placebo group comparisons will be made with the Student's t-test (continuous variables) or Fisher's exact test (categorical variables). A p-value of ≤ 0.05 will be considered statistically significant. For group comparisons of variables that will be analyzed at more than onetime point, Analysis of Variance (ANOVA) for repeated measurements will be used followed by Student's t-test if the ANOVA (group or interaction between group and time) indicated a statistically significant difference ($p \leq 0.05$).

Data Storage and Confidentiality

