fib-tem®	Provides information on fibrinogen level and quality of fibrin polymerization in citrated blood by inhibiting thrombocytes	Reagent contains thrombocyte inhibitor and recalcification reagent. Used in conjunction with ex-tem® test	- Store at +2 - +8°C - Stable until the expiration on label. Vials must be used within 14 days after opening
hep-tem®	Used to monitor the coagulation process via the intrinsic pathway, in the presence of unfractionated heparin, in citrated whole blood specimens	Reagent contains heparinase that inactivates heparin in vitro. Also contains an optimized calcium ion concentration in a buffer to start the coagulation reaction	-- Store at +2-+8°C - Stable until expiration on label. - Reconstituted reagent is stable for 30 days at +2 - +8°C
in-tem®	Used to monitor the coagulation process via the intrinsic pathway in citrated whole blood specimens	Reagent contains an concentration of ellagic acid creating a standardized mild activation of the contact phase through negatively loaded surface. Sample is recalcified with a-tem®	Store at +2-+8°C - Stable until expiration on label. Vials must be used within 8 days after first opening

Figure 2 Transfusion Algorithm

ROTEM Parameters
 CT = Clotting time (sec)
 CFT = Clot formation time (sec)
 MCF = Maximal clot firmness (mm)

Figure 3. Blood Transfusion Protocol

Dosing amounts of the required component therapy will be based on the formula below:

PRBC: Volume required = Blood volume (V) x desired Hct increase / Hct of red cell unit (70%)

FFP: 20 cc/kg

[figure not shown]
Plateletpheresis: 20 cc/kg

Cryoprecipitate: 10 cc/kg

Figure 4. Rotem Experience

ROTEM® Experience

Using Detailed Hemostasis Information

Please note: Results from the ROTEM® delta should not be the sole basis for a patient diagnosis, but should be evaluated together with the patient's medical history, the clinical picture, and if necessary, further coagulation tests.

Risk/Benefit Assessment

Risk Category: Greater than minimal.

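### Fibrinogen level and ROTEM are classed as primary efficacy in a trial that infuses fibrinogen, so a primary endpoint could be met without evidence of less bleeding or transfusion

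*Combined protocol and SAP*

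**What the plan says.** Under Endpoints, the list headed "Primary efficacy endpoints will be estimated as follows" has four unranked bullets: 24-hour bleeding, transfused products by component, hemoglobin, and the laboratory panel "effects of fibrinogen infusion on global hemostasis 2 hr. and 24 hr. after surgery (PT, PTT, INR, fibrinogen level, platelet count and ROTEM analysis"). Factor VII use and dose are then added as primary. Patient Assessment repeats the four bullets in a sentence that begins "Primary efficacy endpoints will be postoperative bleeding during the first 24 hours (hr) after surgery (cc/kg), the total volume and identity of transfused blood products" and runs on to the same laboratory panel, so the classification is not a slip in one place.

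The drug is described in Background: "RiaSTAP is a purified fibrinogen concentrate derived from the plasma of healthy donors". Under Randomization, "Group 1 will receive an infusion of RiaSTAP, right after the termination of CPB at a dose of 70 mg/kg", and Group 2 receives saline. In Figure 1, fib-tem is one of five ROTEM assays, with the indication "Provides information on fibrinogen level and quality of fibrin polymerization in citrated blood by inhibiting thrombocytes". Methods to Minimize Bias concedes that "After review of the ROTEM values, the identity of the study drug may be discernable".

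Purpose of Study and Background state the hypothesis in terms of peri-operative bleeding and transfusion only. Statistical Analyses sets the threshold: "A p-value of ≤ 0.05 will be considered statistically significant". It gives no ranking of the primary variables, no multiplicity rule and no definition of a successful trial.

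**The concern.** One arm is infused with the substance that one primary endpoint measures. For fibrinogen level, the null hypothesis of no difference between arms is therefore expected to be false on pharmacological grounds, whether or not the drug helps. Rejecting it answers a dose-delivery question, not the study question.

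A multiplicity adjustment would not cure this. Such adjustments limit false positives among true nulls, and here the difference may be real but not informative about bleeding. What is at stake is the meaning of the primary efficacy label: the plan as written would permit a report that a primary efficacy endpoint was met when bleeding and transfused volume show nothing.

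**Working it through.** **Plan's own figure.** There is none to reproduce. The document gives 30 patients, 15 per group, with no power statement, effect size or SD. The classification was checked by reading; the arithmetic below is illustrative.

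**Inputs from the document.** Dose 70 mg/kg; 15 per arm; p ≤ 0.05 (taken as two-sided, since sidedness is not stated); cryoprecipitate at 10 cc/kg (Drug protocol, Figure 3) with fibrinogen usually around 15 g/L (Background).

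**Assumptions not in the document.** Plasma volume 40-60 mL/kg, recovery 60-100%, SD of fibrinogen 0.5-0.8 g/L.

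**Step 1: expected rise.** Rise in g/L = dose (mg/kg) × recovery / plasma volume (mL/kg).
- Low: 70 × 0.6 / 60 = 0.70 g/L.
- High: 70 × 1.0 / 40 = 1.75 g/L.
- A less favourable case: blood volume 90 mL/kg and hematocrit 0.30 give plasma 90 × 0.70 = 63 mL/kg; with 40% recovery, 70 × 0.4 / 63 = 0.44 g/L.

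**Step 2: chance of significance with no cryoprecipitate in either arm.** Two-sample t-test, 28 degrees of freedom, noncentrality (rise/SD) × √(15/2).

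| Rise / SD (g/L) | Standardized difference | Significant |
|---|---|---|
| 0.44 / 0.8 | 0.55 | 31% |
| 0.7 / 0.8 | 0.875 | 64% |
| 1.0 / 0.8 | 1.25 | 91% |
| 0.7 / 0.5 | 1.40 | 96% |
| 1.5 / 0.8 | 1.875 | 99.9% |

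A bleeding endpoint with no true effect would be significant 5% of the time.

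**Step 3: allow for cryoprecipitate in controls.** One dose supplies 10 mL/kg × 15 mg/mL = 150 mg/kg of fibrinogen, more than twice the study dose. If a fraction f of controls and nobody in Group 1 receives one dose, the mean contrast is 70 − 150f mg/kg. It is zero at f = 70/150 = 47% and reverses beyond that. Simulating the 15-per-arm t-test over rises of 0.7-1.75 g/L and SDs of 0.5-0.8 g/L, with equal recovery of both products and cryoprecipitate use independent of baseline, gives the chance of a significantly higher level in Group 1:

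| Controls given cryoprecipitate | Significant |
|---|---|
| 0% | 64% to over 99% |
| 10% | 40-91% |
| 20% | 22-59% |
| 30% | about 11-27% |
| 40% | about 5-9% |

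These rates do not depend on the effect on bleeding. In every row below the first, Group 1 uses less cryoprecipitate by construction, yet the fibrinogen endpoint becomes less likely to favor it. The measure can therefore move against the transfusion outcome that it sits beside.

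**Not modelled.** The planned repeated-measures ANOVA that precedes any t-test for the 2 h and 24 h values, the decline of fibrinogen by 24 h, and cryoprecipitate in Group 1.

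**The case against.** The strongest reply is that the wording of the bullet already marks it as pharmacodynamic, that bleeding and transfusion are listed separately and first, and that nowhere does the plan say one significant primary variable makes the trial positive. On that view the defect is a label, and naming a single primary endpoint would settle it together with the multiplicity problem. The premise is right: there is no stated success rule. But the label is primary efficacy in both places, and no text prevents a fibrinogen difference from being reported under it.

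Three further objections stand and limit the point.

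- **Near-certainty is not supported.** A reader might infer that a positive fibrinogen result is almost assured. The 64% to over 99% range holds only with no cryoprecipitate in controls and a single time point. How often controls would receive it is not stated, and the document is not consistent on the trigger: the Drug protocol narrative ties cryoprecipitate to a ROTEM fibrinogen deficiency, while the four scenarios that follow also require significant bleeding. Those passages need to be reconciled.
- **FIBTEM is not purely a delivery check.** Figure 1 says it also reads polymerization quality, and Background describes fibrinogen in these infants as dysfunctional. Whether infused fibrinogen improves clot quality is a genuine question, though not the hypothesized one.
- **ROTEM as a whole is not an assay of the drug.** Of the five listed assays, only fib-tem is described as reporting fibrinogen. PT, PTT, INR and platelet count do not measure it directly either.

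It might also be argued that fibrinogen is a valid surrogate because Background calls preoperative concentration a predictor of bleeding. That does not show that raising it by infusion reduces bleeding in these infants, which is what the trial is meant to test.

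**Conclusion.** The concern holds as a mismatch between the primary efficacy label and the stated hypothesis. It applies most clearly to fibrinogen level, next to FIBTEM, and in part to other ROTEM readings that the transfusion algorithm treats as responsive to fibrinogen. The documents do not support the stronger readings that a positive result is assured or that the whole ROTEM panel is circular.

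The size is uncertain. Under the stated assumptions, the chance of a significant fibrinogen difference runs from under 10% when 40% of controls receive cryoprecipitate to over 99% when none do. A rise of only 0.44 g/L with SD 0.8 g/L lowers the no-cryoprecipitate figure to about 31%. The case for the change does not rest on any one of these figures: at whatever rate it occurs, such a result would not show less bleeding or less component use. This should be corrected before analysis.

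**What to change.** In Endpoints and in Patient Assessment:

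1. Keep 24-hour bleeding and transfused volume under primary efficacy.
2. Move fibrinogen level and the ROTEM readings to a pharmacodynamic heading outside primary efficacy. At a minimum this covers FIBTEM and other readings that the algorithm treats as fibrinogen-responsive, such as hep-TEM CFT, for which cryoprecipitate is one of the listed responses.
3. State that a difference on these measures alone is not evidence of reduced bleeding or transfusion.

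The cost is wording in two sections. Blood samples, time points, sample size and analyses are unchanged. The downside is fewer measures that can be called a positive primary result. The change does not settle multiplicity among the primary variables that remain, which needs its own rule.
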